#### 6.6.1.1.4. Analysis Variable

Change from baseline in the total score of all PUL assessments in the randomization treatment period, including scheduled, unscheduled, and available assessments after treatment discontinuation, up to the targeted week 52 during the On-Study period ([Section 5.3.1.1](#)), will be included in the analysis.

#### 6.6.1.1.5. Population Summary for Treatment Comparison

Treatment difference of Least-square mean (LSMean) and SE at week 52 and corresponding 95% CI will be presented.

The random coefficient linear regression model (RCM), where within-patient errors follow a random coefficient regression model will be performed. The RCM model will include fixed effects of time, treatment, treatment-by-time interaction, with baseline ordinal PUL entry score as covariate. The time in the RCM model will be calculated as the elapsed weeks (considered as a continuous variable with 1 decimal place) from first dose date (or randomization date for subjects who drop out prior to any study medication) to the assessment date. All valid values including from unscheduled visits will be included.

The residual plot from the PROC MIXED output will be examined. If the residual plot shows a systematic pattern rather than a random scatter, then the linearity assumption may not be appropriate. In case of non-linearity, MMRM will be used as the primary analysis method, which is currently listed as one of the sensitivity analyses in next section.

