8.3.4. Efficacy Analyses

The analyses of the efficacy endpoints will be based on subjects in the ITT population.

8.3.4.1. Analysis of Primary Endpoint Change in PUL from Baseline to Week 52

The primary endpoint, Change in the total score of Performance of Upper Limb [(PUL) 2.0 version], from baseline to Week 52 will be analyzed using a random coefficient model with treatment, visit, visit-by-treatment interaction, , and baseline total score of Performance of Upper Limb value as fixed effects; the intercept and linear slope of visit as random effects. The primary analysis will be based on observed data from subjects in the ITT population.

As sensitivity analysis, the analysis of covariance model (ANCOVA) model with Multiple Imputations (ANCOVA –MI) will be also applied. The model will include treatment and baseline total score of Performance of Upper Limb value. The primary analysis will be based on the ITT population.

PUL 2.0 scale:

- The PUL 2.0 scale, total score = 42.
- High Level: Shoulder Dimension, 6 items: Max score = 12
- Mid-level: Elbow Dimension, 9 items: Max score = 17
- Distal level: Wrist and Finger Dimension, 7 items: Max score = 13

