8.3.4.2. Analyses of Secondary Endpoints

Changes in ppFVC and ppPEF from Baseline to Week 52

The Change from baseline to Week 52 in ppFVC will be analyzed using a random coefficient model with treatment, visit, visit-by-treatment interaction, and baseline ppFVC as fixed effects; the intercept and linear slope of visit as random effects. The analysis will be based on observed data from subjects in the ITT population.

The Change from baseline to Week 52 in ppPEF will be analyzed using a random coefficient model with treatment, visit, visit-by-treatment interaction, and baseline ppPEF as fixed effects; the intercept and linear slope of visit as random effects. The analysis will be based on observed data from subjects in the ITT population.

Change in the Grip Strength of the Hands from baseline to Week 52, assessed by Hand Held Myometry (HHM)

The Change from baseline to Week 52 in grip strength of the hands will be analyzed using a random coefficient model with treatment, visit, visit-by-treatment interaction, and baseline value as fixed effects; the intercept and linear slope of visit as random effects. The analysis will be based on observed data from subjects in the ITT population.

Change in Left Ventricular Ejection Fraction percentage (LVEF %) from Baseline to Week 52, Assessed by MRI.

Summary of Listing and the analyses of the change from baseline to week 52 in LVEF (%) assessed by MRI will be conducted in the ITT population.

The change from baseline to Week 52 in left ventricular ejection fraction percentage (LVEF%), as assessed by MRI will be analyzed using a random coefficient model with treatment, visit, visit-by-treatment interaction, and baseline value as fixed effects; the intercept and linear slope of visit as random effects.

As an exploratory endpoint, the dichotomous responder (proportion of patients with change from baseline in LVEF% ≥ 0 at Week 52) will be summarized and analyzed. The logistic regression model will be used to compare the proportion of subjects with change from baseline in LVEF% ≥ 0 . The model will include treatment and baseline LVEF%.

For other secondary endpoints, MMRM model will be used in continuous variables; logistic regression model in binary variables; Cox regression model in time-to-event variables. The analysis models will include appropriate baseline factors. Other methods will be applied as appropriate.

Detailed analyses of all secondary endpoints will be clearly outlined in the SAP.

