#### Covariance Structure Strategy

The unstructured covariance structure for the within-patient errors in the model will be applied first. The by-treatment-group option is included to the covariance pattern to improve the model efficiency.

If the algorithm for unstructured covariance pattern does not converge, the following covariance structures will be tested in sequence until the model converges: heterogeneous Toeplitz, homogeneous Toeplitz, first-order autoregressive, compound symmetry, and variance component. The sandwich estimator will be used if there is convergence issue. When the random effects model does not converge or does not have a positive definite Hessian, the fixed effects instead of random effects will be performed instead. The Least Square Mean (LSMean) (SE) and 95% CI estimated changes from baseline to Week 52 will be presented.

Sample SAS code:

```
PROC MIXED DATA = XXX;
  CLASS TRTPN SUBJID ItemAgrp;
  MODEL CHG = TRTPN AWK TRTPN*AWK ItemAgrp / RESIDUAL CL COVB DDFM=KR;
  RANDOM AWK / SUBJECT =SUBJID TYPE=UN GROUP= TRTPN;
  LSMEANS TRTPN / at AWK = 52 PDIFF CL;
  ODS OUTPUT LSMEANS=MIXLSMNS DIFFS=MISDIFS;
RUN;
```

(Note: ItemAgrp denotes the categorical Item A (or PUL entry) scores at baseline)

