**6.6.2.1.1.3. Intercurrent Event Handling Strategy**

Same as [Section 6.6.1.1.3](#)

**6.6.2.1.2. Analysis Variables****6.6.2.1.2.1. Change in Percent Predicted Forced Vital Capacity (ppFVC) from baseline to Week 52, assessed by spirometry****6.6.2.1.3. Change in the total score of Mid-level of PUL from baseline to Week 52 Population Summary for Treatment Comparison**

Same as [Section 6.6.1.1.5](#).

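### The SAP's random coefficient model replaces each endpoint's own baseline with the PUL entry item, and SAP Section 7 does not disclose it

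*SAP*

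**What the plan says.** **Protocol.** The primary RCM (8.3.4.1) has "baseline total score of Performance of Upper Limb value as fixed effects". The ppFVC model (8.3.4.2) has "treatment, visit, visit-by-treatment interaction, and baseline ppFVC as fixed effects", and the ppPEF model has "treatment, visit, visit-by-treatment interaction, and baseline ppPEF as fixed effects". The PUL subscores, Mid-level among them, are exploratory in the protocol and go into an MMRM that includes the baseline of the subscore analysed (8.3.5).

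**SAP.** The primary RCM (6.6.1.1.5) has "fixed effects of time, treatment, treatment-by-time interaction, with baseline ordinal PUL entry score as covariate". Its code is "MODEL CHG = TRTPN AWK TRTPN*AWK ItemAgrp / RESIDUAL CL COVB DDFM=KR", where `ItemAgrp` is the categorical Item A (PUL entry) score. There is no term for the baseline PUL total.

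SAP 6.6.2.1 puts ppFVC and Mid-level PUL under the RCM. Its last heading, "Change in the total score of Mid-level of PUL from baseline to Week 52 Population Summary for Treatment Comparison", is followed only by a reference back to 6.6.1.1.5. SAP Table 1 makes these tests 2 and 3 of the fixed sequence. The High and Distal subscores (6.6.3.1), ppFEV1 (6.6.3.3) and ppPEF (6.6.3.4) are sent to the same model.

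SAP 6.6.1.1.5 also provides a fallback: "In case of non-linearity, MMRM will be used as the primary analysis method". The text of that MMRM (6.6.1.2.1.5) speaks of baseline values as covariates, but its code contains `ItemAgrp` alone.

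**The concern.** The own baseline is the covariate the protocol chose and usually the most useful one for a change score. In the SAP's RCM it has been replaced, not supplemented. For PUL the replacement is at least a related upper-limb measure. For ppFVC it is a rating of arm function standing in for baseline lung function.

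A programmer who follows 6.6.2.1 as written and one who follows protocol 8.3.4.2 would fit different models to the first test after the primary. The ITT, on-treatment, per-protocol and subgroup RCM analyses refer back to the same specification, and PUL and ppFVC enter all three composite z-scores, so the ambiguity spreads. If it is settled after unblinding, the choice of covariate could look data-driven.

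**Working it through.** **1. The plan's own figures.** For a two-sided two-sample t-test with difference 2.0, SD 2.9 and alpha 0.05 (SAP 3.3), the noncentrality is 2.0 / (2.9 × √(2/n)).
- n = 46 per arm (92): 2.0 / 0.605 = 3.31 on 90 df, power 90.5%.
- n = 41 per arm (82): 2.0 / 0.641 = 3.12 on 80 df, power 87.0%.

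Both stated figures (90% at 92; 87% at 82, SAP Section 7) reproduce. The calculation has no covariate, so this point does not alter it.

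**2. Baseline covariate by endpoint.**

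| Endpoint | Protocol | SAP, read literally |
|---|---|---|
| PUL total (test 1) | own baseline, RCM | Item A (6.6.1.1.5) |
| ppFVC (test 2) | own baseline, RCM | Item A by reference (6.6.2.1) |
| Mid-level PUL (test 3) | own baseline, MMRM | Item A by reference (6.6.2.1) |
| Grip strength (test 4) | own baseline, RCM | own baseline, MMRM code (6.6.2.2.3) |
| LVEF% (test 5) | own baseline, RCM | own baseline, ANCOVA (6.6.2.3.3) |
| High and Distal PUL | own baseline, MMRM | Item A by reference (6.6.3.1) |
| ppPEF | own baseline, RCM | Item A by reference (6.6.3.4) |
| ppFEV1 | no model given | Item A by reference (6.6.3.3) |

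**3. SAP Section 7.** It lists the mITT set, the sample-size update, the testing order, MMRM to RCM for the High and Distal subscores, MMRM to ANCOVA for the MRI endpoints, the added sensitivity analyses, the composite, and Mid-level PUL as a new secondary. No covariate change appears. The move of Mid-level PUL from MMRM to RCM is not listed either.

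**4. Size.** The documents give no correlation r between baseline and change, so this step is illustrative.
- Model: the SAP's coded structure, change on treatment, week, treatment × week and Item A (5 levels, as mITT keeps scores 2 to 6), with and without own baseline. The random effect is slope only, by arm, as in "RANDOM AWK / SUBJECT =SUBJID TYPE=UN GROUP= TRTPN". REML; difference read at Week 52.
- Design: 41 per arm; weeks 12, 22, 32, 42, 52 for ppFVC (SAP Table 8) and 16, 28, 40, 52 for PUL (Table 9); 8,000 simulated trials per setting.
- Assumed: Week 52 change variance 1; visit noise variance 0.1 or 0.2; correlation of baseline with the latent Item A score 0 or 0.5 for ppFVC and 0.8 or 0.9 for PUL.

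Percent fall in the variance of the Week 52 difference when own baseline is added:

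| Setting | r = 0.2 | r = 0.3 | r = 0.5 |
|---|---|---|---|
| ppFVC, baseline predicts slope | 0.6-1.7 | 1.6-4.3 | 6.2-12.9 |
| ppFVC, baseline shifts level | 3.2-4.1 | 7.6-10.4 | 21.9-27.2 |
| PUL, baseline predicts slope | 0.2-0.6 | 0.8-2.1 | 3.1-7.6 |
| PUL, baseline shifts level | 0.5-2.4 | 1.9-4.2 | 8.5-13.2 |

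The Monte Carlo standard error is 0.1 to 0.9 percentage points. The mean difference stays within 0.005 of zero with or without the covariate. As a cross-check, the simple rule of variance × (1 − r²) gives falls of 4%, 9% and 25%, inside the ppFVC level ranges.

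**5. In patients.** Equivalent extra patients = 82 × (1/(1 − v) − 1), where v is the fall in variance. At r = 0.3:
- ppFVC: v = 1.6% gives 1.3; v = 10.4% gives 9.5.
- PUL: v = 0.8% gives 0.7; v = 4.2% gives 3.6.

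**6. Chance imbalance in ppFVC.** With an assumed baseline SD of 8 to 11.5 points (the upper value is a uniform spread over the 45-85 entry range, 40/√12), the SE of the baseline difference is SD × √(2/41) = 1.8 to 2.6 points. With an assumed slope of change on baseline of 0.1 to 0.3 per point, a one-SE imbalance left unadjusted moves the Week 52 difference by about 0.2 to 0.8 points.

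**The case against.** The best defence is that the ppFVC part is a drafting shortcut. SAP Section 1 presents the SAP as an elaboration of the protocol's analyses, Section 7 declares no covariate change, and grip strength and LVEF% keep their own baseline. That is plausible. But it is a general statement that puts no covariate back into the model, so the specification still has to be corrected.

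For PUL, Section 7 cites published advice that entry scores be considered in design and analysis. This makes Item A a defensible covariate, but Section 7 uses it to justify the mITT set, never mentions dropping the baseline total, and gives no reason to use an arm item for spirometry.

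Several limits stand:
- Every size above depends on an assumed r. A small run for ppFVC at r = 0.1 (700 trials, baseline predicting slope) found a gain of about 0%, and the 45-85 entry range tends to hold r down.
- The upper ends need a level effect. Averaging the PFT baseline over Screening and Day 0 (protocol 6.2.5) removes one source of that, although SAP Table 8 points to the last-value rule in 5.3.2.
- ppFEV1 has no protocol model to depart from, and the High and Distal subscores, ppFEV1 and ppPEF are outside the testing sequence.
- The MI-ANCOVA text already names baseline PUL, and its code has an open `COVARIATES` slot. That needs a name and is not an error.
- Using both the PUL total and Item A matches neither document's RCM, and the gain for PUL is small.

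**Conclusion.** The point holds. As written, the SAP's RCM adjusts only for the PUL entry item. That carries over to ppFVC and Mid-level PUL, departs from the protocol's own-baseline adjustment, and is not disclosed in Section 7.

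The consequence is lost precision and an ambiguous model for gated tests. Validity, sample size and stated power are not affected. The loss falls mainly on ppFVC. At an assumed r of 0.3 it is most plausibly in the lower half of 1.6-10.4% of variance; for PUL it is small, because Item A already carries much of the baseline information. The case for correcting it does not depend on the upper figures: the departure is undisclosed and costs almost nothing to repair. It should be fixed.

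**What to change.** Before unblinding:
- **6.6.1.1.5 and its code:** add the continuous baseline PUL total alongside `ItemAgrp`.
- **6.6.2.1:** name baseline ppFVC for ppFVC and the baseline Mid-level score for Mid-level PUL.
- **6.6.3.1, 6.6.3.3, 6.6.3.4:** name the own baseline for the High and Distal subscores, ppFEV1 and ppPEF.
- **6.6.1.2.1.5:** add the baseline PUL total to the MMRM code, since this model may become primary.
- **6.6.1.2.3.5:** name the baseline PUL total in the `COVARIATES` slot.
- **Section 7:** if Item A alone is intended for any endpoint, list it with a reason. Also list the move of Mid-level PUL from MMRM to RCM.

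The cost is a few words of text and one degree of freedom per model. All the values are already collected, and no extra patients are needed.

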### 3.3. Sample Size Determination

This section is updated based on latest publications and the study enrollment.

This study is planned to enroll a total of approximately 92 subjects with a 1:1 randomization ratio of assigning to pamrevlumab or placebo, respectively. With Performance of Upper Limb (PUL) version 2.0, the sample size of 92 subjects is needed to detect a treatment difference of 2.0 between treatment arms in change from baseline in the total score of PUL at Week 52, assuming a standard deviation of 2.9 with a 90% power, based on a two-sided two-sample t-test at the alpha level of 0.05. A sample size of 82 subjects will provide the study with at least 85% power to detect the same assumed treatment difference.

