**PUL 2.0 scale:**

- The PUL 2.0 scale, with maximum total score = 42

- High Level: Shoulder Dimension, 6 items: Max score = 12
- Mid-level: Elbow Dimension, 9 items: Max score = 17
- Distal level: Wrist and Hand Dimension, 7 items: Max score = 13

Only 1 item in each domain is allowed missing. The score of the missing item will be imputed by the mean of the non-missing items in the domain. If the total score of any domain is missing (the high-level domain only applies to subjects with Item A score  $\geq 3$ ), then the total score will be missing. The total score of PUL is the sum of the total scores of the three domains (if Item A score  $\geq 3$ ) or two domains (Mid-level and Distal level, if Item A score  $< 3$ ).

The last measurement prior to first dose of study drug from Muscle Function Tests (MFTs) at Day 1 will be used to establish baseline.

The primary efficacy endpoint will be analyzed using mITT as the primary analysis set.

The hypothesis to be tested for the primary efficacy analysis is:

**H0:** Change from Baseline in the total score of PUL at Week 52 for the pamrevlumab arm = Change from Baseline in the total score of PUL at Week 52 for the placebo group

Versus:

**H1:** Change from Baseline in the total score of PUL at Week 52 for the pamrevlumab arm  $\neq$  Change from Baseline in the total score of PUL at Week 52 for the placebo group

H0 will be tested at the two-sided alpha = 0.05 level of significance and will be rejected if the p < 0.05 from the test.

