##### 6.6.1.2.6.5. Population Summary for Treatment Comparison

If linear assumption was met, the RCM linear regression model as described in [Section 6.6.1.1.5](#) will be performed; otherwise, ANCOVA model as described in [Section 6.6.1.2.3.5](#) will be performed.

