##### **6.6.1.2.7.5. Population Summary for Treatment Comparison**

If the linear assumption was met, the RCM linear regression model as described in [Section 6.6.1.1.5](#) will be performed; otherwise, the ANCOVA model as described in [Section 6.6.1.2.3.5](#) will be performed.

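### The trigger for replacing the RCM by MMRM as primary model has no criterion and need not be settled before unblinding, so no single primary test is fixed

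*SAP*

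**What the plan says.** SAP 6.6.1.1.5 names the RCM as primary and has its residual plot inspected. The rule is: "If the residual plot shows a systematic pattern rather than a random scatter, then the linearity assumption may not be appropriate". The consequence follows: "In case of non-linearity, MMRM will be used as the primary analysis method". MMRM otherwise stands as a sensitivity analysis (SAP 6.6.1.2.1).

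The sample code under Covariance Structure Strategy fits treatment (`TRTPN`), treatment by time and a covariance grouped by treatment. The same call requests the residuals and the treatment difference at Week 52.

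The primary hypothesis (SAP 6.6.1) "will be tested at the two-sided alpha = 0.05 level of significance", and it opens the fixed sequence in SAP Table 1.

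The fallback when linearity fails is not the same everywhere:
- **Primary and subgroup analyses:** MMRM (SAP 6.6.1.1.5 and 6.6.4).
- **On-treatment analysis (SAP 6.6.1.2.6.5):** "If linear assumption was met, the RCM linear regression model as described in" the primary section is used, otherwise ANCOVA.
- **Per-protocol analysis (SAP 6.6.1.2.7.5):** "If the linear assumption was met, the RCM linear regression model as described in" the primary section is used, otherwise ANCOVA.
- **ppFVC and Mid-level PUL (SAP 6.6.2.1.3):** only a cross-reference to 6.6.1.1.5.

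Protocol 8.3.4.1 has the RCM alone. SAP Section 7 records MMRM as an added sensitivity analysis and does not record that it can become primary.

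**The concern.** Two competent statisticians could read the same plot and declare different primary analyses. Signing the SAP before database lock fixes the words of the rule but not its outcome. As the code is written, the plot needs real treatment codes and comes from the run that gives the Week 52 result. If RCM and MMRM fall on opposite sides of 0.05, the plan cannot show which one counts, and the sponsor could not demonstrate that the choice was independent of the p-value. Every gated secondary endpoint depends on that one decision, and it cannot be repaired after unblinding.

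The diagnostic is also not a sharp one for this scale. PUL items are scored in whole numbers, so apart from imputed items the change scores are integers. Their residuals fall in bands against the fitted values even when the trend is linear.

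**Working it through.** **1. The plan's own figures.** Inputs from SAP 3.3: equal allocation, a target difference of 2.0 points, and the rest as stated there: "assuming a standard deviation of 2.9 with a 90% power, based on a two-sided two-sample t-test at the alpha level of 0.05". With noncentrality 2.0 / (2.9 × √(2/n)):
- n = 46 per arm: 3.307, 90 df, power 90.5%. The stated 92 subjects for 90% reproduces.
- n = 41 per arm: 3.123, 80 df, power 87.0%. This agrees with the 87% for 82 subjects in SAP Section 7 and with the at-least-85% in SAP 3.3.

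The sample-size figures are not in error.

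**2. What each model estimates.** PUL visits are Weeks 16, 28, 40 and 52 (SAP Table 9). With complete data, the RCM mean at Week 52 is the per-subject fitted line at Week 52. Visit times average 34, the deviations are −18, −6, 6, 18, and their squares sum to 720. The weight of each visit is 1/4 + (52 − 34) × deviation / 720, which gives −0.2, 0.1, 0.4, 0.7. Unstructured MMRM uses the observed Week 52 change, with weights 0, 0, 0, 1.

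**3. Precision.** Split the Week 52 variance 2.9² = 8.41 into a random-slope part and a residual part s², where s is assumed because the documents give no value. The squared RCM weights sum to 0.04 + 0.01 + 0.16 + 0.49 = 0.70, so the RCM variance is 8.41 − 0.30s². At 41 per arm and a linear course:
- s = 0.8: variance 8.218, SD 2.867, power about 88%.
- s = 2.3: variance 6.823, SD 2.612, power about 93%.
- MMRM at any s: SD 2.9, power 87%.

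**4. Error of the choice.** Simulation with 41 per arm, complete data and two-sample t-tests on the two contrasts. There were 60,000 null trials per row (20,000 for s = 2.3). The last column uses a linear effect of 2.0 at Week 52.

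| s (assumed) | RCM alone | MMRM alone | Switch on pooled curvature, p<0.10 | Better of the two | Disagree at difference 2.0 |
|---|---|---|---|---|---|
| 0.8 | 4.8% | 4.8% | 4.8% | 5.4% | 2.5% |
| 1.2 | 5.1% | 5.1% | 5.0% | 6.1% | 4.0% |
| 1.6 | 5.0% | 5.0% | 5.0% | 6.4% | 5.4% |
| 2.0 | 4.9% | 4.9% | 4.9% | 6.7% | 6.9% |
| 2.3 | 5.2% | 5.0% | not run | 7.2% | about 8% |

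Adding a true pooled curvature changes little: 5.1% for the pooled switch and 6.2% to 6.6% for the better of the two. Switching on curvature in either arm gives 4.9% to 5.3%. The ceiling for two independent tests would be 1 − 0.95² = 9.75%. These two tests correlate at 0.93 to 0.99, so the worst case lies well below that.

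**5. Arms equal at Week 52 but different on the way.** An assumed transient difference of 1.0 to 1.5 points shifts the RCM estimate by 0.2 to 0.3. RCM alone then rejects in 5.9% to 7.5% of trials, MMRM in about 5%, and the better of the two in 7.5% to 9.5%.

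**The case against.** The strongest reply is that little is left open. The RCM is the default, there is one named alternative and one direction of switch, and each model has a written form and covariance sequence. A statistician who follows the diagnostic honestly keeps about 5%, as step 4 shows. The worst case assumes someone who ignores the plot and takes the smaller p-value. This all stands, and it limits what can be claimed.

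Four stronger readings are tempting, and the documents do not support them:
- **That the primary analysis is not pre-specified.** Both models and the default are; only the trigger is missing.
- **That the SAP has the choice made unblinded.** It is silent on blinding at this step. The inference rests on treatment being in the plotted model and on the absence of any blinded step.
- **That the error rate is inflated.** It is not guaranteed, which is different. Under the full null, inflation needs a choice that follows the result.
- **That the RCM overstates early effects and understates late ones.** This depends on the profile. With the weights above, effects of 1, 2, 2, 2 give −0.2 + 0.2 + 0.8 + 1.4 = 2.2, and 0, 0, 1, 2 give 0.4 + 1.4 = 1.8. A full effect of 2.0 from Week 16 gives exactly 2.0.

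Nor does anything show that banded residuals would be taken for non-linearity. The ANCOVA fallback affects only sensitivity analyses outside Table 1, so it is a consistency matter and does not bear on the 5%. Whether the switch reaches ppFVC and Mid-level PUL is unclear, because a bare cross-reference carries it. None of this supplies a criterion or a time for the decision.

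**Conclusion.** The point holds in this form: the trigger for changing the primary model is undefined, and nothing requires it to be settled before unblinding. No single primary test is therefore fixed, and the 5% level is not guaranteed. The size is modest: near 5% if the switch tracks curvature objectively, 5.4% to 7.2% at worst under the full null, and about 3% to 8% of trials at the planned effect in which the choice decides significance.

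These figures assume complete data, 41 per arm, a Week 52 SD of 2.9 and residual SDs of 0.8 to 2.3. They leave out the entry-score covariate, missing data, the Kenward-Roger adjustment and the covariance by treatment group, so they indicate size only. The point still deserves correction because it concerns the one test that gates all the others, and the remedy is cheap.

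**What to change.** Delete the residual-plot switch and name one primary model before unblinding:
- **MMRM primary, RCM as sensitivity.** This tests the Week 52 difference without assuming linearity and keeps the stated 87% power at 82 subjects. SAP 6.6.1.2.1.5 should then be reconciled, since its text adjusts for baseline values and its code for the entry-item category.
- **RCM primary, MMRM as sensitivity.** This fixes the test too, but leaves the Week 52 contrast dependent on linearity (step 5).

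Alternatively, choose before database lock on blinded pooled data: fit the RCM without treatment terms, add time squared, use MMRM if its p<0.05, and record the choice in a signed note. A rerun of this rule gave an error of 5.0% to 5.1%. It has limited sensitivity to curvature in one arm: for the 1, 2, 2, 2 profile it triggers in about 59% of trials at residual SD 1.0 and about one in five at 2.0.

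In any case, report both models, list the rule in SAP Section 7, state whether it applies to ppFVC and Mid-level PUL, and have the on-treatment and per-protocol analyses use whichever model is primary instead of ANCOVA.

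The cost is SAP wording, at most one blinded run, and possibly a little power if MMRM is fixed and the course is linear (about 87% against 88% to 93% for the RCM under the assumed variances).
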